4.5.6 Electrocardiograms

Single ECG recordings will be obtained at screening and specified timepoints, as outlined in the schedule of activities (see [Appendix 1–Appendix 3](#)), and may be obtained thereafter at unscheduled timepoints as at the investigator's discretion.

All ECG recordings must be performed using a standard high-quality, high-fidelity digital electrocardiograph machine equipped with computer-based interval measurements.

Lead placement should be as consistent as possible. ECG recordings must be performed after the patient has been resting for at least 10 minutes. All ECGs are to be obtained prior to other procedures scheduled at that same time (e.g., vital sign measurements, blood draws) and should not be obtained within 3 hours after any meal. Circumstances that may induce changes in heart rate, including environmental distractions (e.g., television, radio, conversation) should be avoided during the pre-ECG resting period and during ECG recording.

For safety monitoring purposes, the investigator or delegate must review, sign, and date all ECG tracings. Paper copies of ECG tracings will be kept as part of the patient's permanent study file at the site.

4.5.7 Clinical Outcome Assessments

PRO instruments will be completed to assess the clinical efficacy of AT-527 compared with placebo. In addition, PRO instruments will enable the capture of each patient's direct experience with AT-527.

PRO data will be collected through use of the following instruments: COVID-19 Symptom Diary and Patient Global Impression of Severity (PGIS).

4.5.7.1 Data Collection Methods for Clinical Outcome Assessments

PRO instruments will be self-administered at specified timepoints during the study (see the schedules of activities in [Appendix 1–Appendix 3](#)). At the clinic, instruments will be administered before the patient receives any information on disease status, prior to the performance of non-PRO assessments, and prior to the administration of study treatment unless otherwise specified.

PRO instruments, translated into the local language as appropriate, will be provided by the Sponsor in pre-printed booklets to enable the instrument to be administered. The booklets will be labeled to capture timepoint of administration.

Patients should be given the following instructions for completing PRO instruments at home or in the clinic:

- Patients should complete the instruments in a quiet area with minimal distractions and disruptions.
- Patients should answer questions to the best of their ability; there are no right or wrong answers.
- Patients should not obtain advice or help from others (e.g., family members or friends) when completing the instruments.

4.5.7.2 Description of Clinical Outcome Assessment Instruments

COVID-19 Symptom Diary

The COVID-19 Symptom Diary (see [Appendix 5](#)) is adapted from a general influenza-like illness symptom patient diary. The diary will be used to characterize key symptoms recognized as attributable to COVID-19 illness per FDA guidance (FDA 2020) as well as to document the treatment benefit of AT-527. The COVID-19 Symptom Diary is composed of 14 individual symptom item questions, each with a 2- or 4-point Likert response option.

As outlined in the schedules of activities ([Appendix 1–Appendix 3](#)), the COVID-19 Symptom Diary will be administered on paper and completed in its entirety by the patient twice a day (morning and evening) on Days 1–14 and once a day in the evening on Days 15–28. Patients will be provided with separate versions of the diary for the Days 1–14 assessments (morning vs. evening) and Days 15–28 assessment (evening).

Patient Global Impression of Severity

The PGIS (see [Appendix 5](#)) is a single item assessment of a patient's impression of severity of his or her COVID-19 symptoms over the course of the study and is administered in conjunction with the COVID-19 Symptom Diary. Change in COVID-19 symptoms is rated on a 4-point Likert scale from "none" (0) to "severe" (3).

Additional COVID-19 Related Assessment

Patients will measure their temperature twice a day on Days 1–14 and once a day on Days 15–28. Temperature will be recorded as an additional entry in the COVID-19 Symptom Diary.

4.5.8 Optional Blood Samples for Whole Genome Sequencing (Patients at Participating Sites)

At participating sites, optional blood samples will be collected from consenting patients for DNA extraction to enable whole genome sequencing (WGS) to identify variants that are predictive of response to study drug, are associated with progression to a more severe disease state, are associated with susceptibility to developing adverse events, can lead to improved adverse event monitoring or investigation, or can increase the knowledge and understanding of disease biology and drug safety. Research will be aimed at exploring inherited characteristics. The samples may be sent to one or more laboratories for analysis.

Collection and submission of blood samples for WGS is contingent upon the review and approval of the exploratory research by each site's Institutional Review Board/ Ethics Committee (IRB/EC) and, if applicable, an appropriate regulatory body. If a site has not been granted approval for WGS, this section of the protocol (Section [4.5.8](#)) will not be applicable at that site.

The Informed Consent Form will contain a separate section that addresses optional blood samples for WGS. A separate, specific signature will be required to document a patient's agreement to provide optional blood samples. The investigator should document whether or not the patient has given consent to participate and (if applicable) the date(s) of consent, by completing the Optional Whole Genome Sequencing Informed Consent/Withdrawal eCRF.

Genomics is increasingly informing researchers' understanding of disease pathobiology. WGS provides a comprehensive characterization of the genome and, along with clinical data collected in this study, may increase the opportunity for developing new therapeutic approaches or new methods for monitoring efficacy and safety or predicting which patients are more likely to respond to a drug or develop adverse events. Data will be analyzed in the context of this study but will also be explored in aggregate with data from other studies. The availability of a larger dataset will assist in identification and characterization of important biomarkers and pathways to support future drug development.

For sampling procedures, storage conditions, and shipment instructions, see the laboratory manual.

Blood samples collected for WGS are to be stored until they are no longer needed or until they are exhausted. However, the storage period will be in accordance with the IRB/EC–approved Informed Consent Form and applicable laws (e.g., health authority requirements).

Refer to Section [4.5.5](#) for details on use of samples after patient withdrawal, confidentiality standards for data, and availability of data from biomarker analyses.

4.6 TREATMENT, PATIENT, STUDY, AND SITE DISCONTINUATION

4.6.1 Study Treatment Discontinuation

Patients must permanently discontinue study treatment if they experience any of the following:

- Any medical condition that the investigator or Sponsor determines may jeopardize the patient's safety if he or she continues to receive study treatment
- Investigator or Sponsor determination that treatment discontinuation is in the best interest of the patient
- Pregnancy
- Any event that meets stopping criteria defined in Section [3.1](#)

The primary reason for study treatment discontinuation should be documented on the appropriate eCRF. Patients who discontinue study treatment prematurely will not be replaced.

Patients who discontinue study drug prematurely will complete assessments as indicated in the schedules of activities (see [Appendix 1–Appendix 3](#)).

Refer to the schedules of activities (see [Appendix 1–Appendix 3](#)) for details on follow-up assessments to be performed for patients who permanently discontinue study treatment. If a patient requests to be withdrawn from treatment or follow-up assessments, this request must be documented in the source documents and signed by the investigator.

4.6.2 Patient Discontinuation from the Study

Patients who discontinue from study participation will have an early termination visit 7 (± 2) days after their final dose of study drug. Patients who discontinue from the study after Day 14 will not be required to complete an early termination visit.

Patients have the right to voluntarily withdraw from the study at any time for any reason. In addition, the investigator has the right to withdraw a patient from the study at any time.

Reasons for patient discontinuation from the study may include, but are not limited to, the following:

- Patient withdrawal of consent
- Study termination or site closure
- Adverse event
- Loss to follow-up
- Patient non-compliance, defined as failure to comply with protocol requirements as determined by the investigator or Sponsor

Every effort should be made to obtain a reason for patient discontinuation from the study. The primary reason for discontinuation from the study should be documented on the appropriate eCRF. If a patient requests to be withdrawn from the study, this request must be documented in the source documents and signed by the investigator. Patients who withdraw from the study will not be replaced.

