- Time to alleviation of COVID-19 symptoms, defined as the length of time taken from start of treatment to the point at which the following criterion is met and maintained for at least 21.5 hours: Score of 0 or 1 on Items 1–12 of the COVID-19 Symptom Diary (without consideration for presence of pre-existing symptoms)
- Time to alleviation of COVID-19 symptoms, defined as the length of time taken from start of treatment to the point at which the following criterion is met and maintained for at least 43 hours: Score of 0 or 1 on Items 1–12 of the COVID-19 Symptom Diary (without consideration for presence of pre-existing symptoms)
- Duration of fever, defined as the time to return to an afebrile state (temperature $\leq 37.5^{\circ}\text{C}$) maintained for at least 21.5 hours
- Frequency of COVID-19-related complications (death, hospitalization, radiologically confirmed pneumonia, acute respiratory failure, sepsis, coagulopathy, pericarditis, myocarditis, cardiac failure)
- *Frequency of hospitalizations and death (all cause)*
- Time to alleviation of an individual symptom, defined as the time taken from the start of treatment to the point at which the following criterion is met and maintained (for each individual symptom) for at least 21.5 hours:
 - Score of 0 or 1 for Items 1–12 of the COVID-19 Symptom Diary
 - Score of 0 for Items 13 and 14 of the COVID-19 Symptom Diary

All secondary endpoints will be analyzed descriptively and summary statistics will be presented. For time to event endpoints, a Kaplan-Meier plot and the median time to response will be presented along with CIs. For proportion, frequency and incidence endpoints, the number, proportion and difference in proportions along with CIs will be presented. For area under the curve (AUC) endpoints, summary statistics will be presented. Any exploratory statistical testing will be specified in the SAP as appropriate.

Rules for missing data will be specified in the SAP.

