Appendix 1: Schedule of Activities for Cohort A

COVID-19=coronavirus disease 2019; ET=early termination; PK=pharmacokinetic; RT-PCR=reverse-transcription polymerase chain reaction; SARS-CoV-2=severe acute respiratory syndrome coronavirus-2; PRO=patient-reported outcome; UV=unscheduled visit.

Notes: On treatment days (Days 1–5), all assessments should be performed prior to dosing, unless otherwise specified.

- ^a Screening assessments may be performed up to 72 hours prior to Day 1 or on Day 1.
- ^b An unscheduled visit represents a visit that is not specified by the protocol but is determined to be necessary by the investigator or Sponsor (e.g., for evaluation of an adverse event). Assessments (including PK sample collection) should be performed as clinically indicated. For unscheduled visits occurring after Day 7, PK sample collection is not required.
- ^c Patients who discontinue study drug prematurely will continue to complete assessments as indicated until the end of the study. Patients who discontinue from study participation will have an early termination visit 7 (± 2) days after their final dose of study drug. Patients who discontinue from the study after Day 14 will not be required to complete an early termination visit.
- ^d Required follow-up information will be collected via telephone call at Day 14 (± 2 days) and Day 33 (± 3 days).
- ^e Informed consent must be documented before any study-specific screening procedure is performed.
- ^f For patients at participating sites who have provided written or electronic informed consent to participate in mobile nursing visits, this assessment or procedure may be performed by a trained nursing professional at the patient's home.
- ^g COVID-19 Symptom Diary includes questions regarding symptoms (Items 1–14) and the Patient Global Impression of Severity. On assessment visit days, questionnaires will be self-administered before the patient receives any information on disease status, prior to the performance of non-PRO assessments, and prior to the administration of study treatment. On Day 1, the first diary questionnaire should be completed prior to the first dose. On Days 1–14, the questionnaire (including recording of temperature) should be completed twice a day (morning and evening) at the same time each day.
- ^h On Days 15–28, the questionnaire (including recording of temperature) should be completed once a day in the evening at the same time each day.

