5.2 PARTICIPANT DISPOSITION

Disposition summaries will be based on the ITT population.

The number of patients who enroll, discontinue, or complete the study will be summarized by treatment group and pooled placebo group. Summaries may also be produced for each individual placebo group. Reasons for premature study withdrawal will be listed and summarized by treatment group. Major protocol deviations (PDs) will be listed and evaluated for their potential effects on the interpretation of study results.

Patients will not be excluded from the analysis populations based on major PDs unless they do not otherwise meet the definitions for each population. Sensitivity analyses evaluating the impact of major PDs may be conducted if a large number of major PD's are observed during the study.

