These endpoints will be summarized using descriptive statistics by treatment group, as well as Kaplan-Meier plots where appropriate. The median time to response will be presented along with the 80% CI. For all cohorts, the efficacy time to event endpoints will be described through Day 28 between the AT-527 group and the combined placebo group from all available cohorts using the mITTi population.

A summary of the symptom severity for each symptom in the COVID-19 symptom diary will be provided at baseline, Day 14 and Day 28 for each treatment group and pooled placebo group. Day 14 (morning) assessments are to be used for the Day 14 summary. If the morning sample is missing, the evening sample will be used.

For efficacy time to event endpoints, deaths will be right censored at Day 28. Consequently, for these endpoints, participants censored on Day 28 reflect two different states, death and failure to meet the improvement outcome criterion. Therefore, it is

important to understand the outcome in the context of the number and timing of deaths by treatment group.

Intercurrent events are those that occur after treatment initiation and either preclude observation of the variable or affect its interpretation. Intercurrent events and missing data will be accounted for through censoring rules, as described in [Table 9](#) below.

Table 9 Efficacy Time to Event Censoring

Event	Censor	Date and Time
Death prior to meeting endpoint	Yes	Final timepoint on Day 28
Discontinuation or lost to follow-up up to Day 28 for any reason prior to meeting endpoint	Yes	Last observed COVID-19 symptom diary assessment
Do not meet the endpoint	Yes	Final timepoint on Day 28

Frequency efficacy endpoints include:

- **Frequency of COVID-19-related complications**
 - COVID-19-related complications include: death, hospitalization, radiologically confirmed pneumonia, acute respiratory failure, sepsis, coagulopathy, pericarditis, myocarditis, and cardiac failure.

For frequency efficacy endpoints, the number, proportion and difference in proportions between the AT-527 group and the pooled placebo group from all available cohorts, along with 80% CIs will be presented by treatment group.

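### Patients who leave the study have no scheduled outcome contact after one early visit at most, and the hospitalization, death and complication proportions have no rule for incomplete follow-up

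*Protocol*

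**What the plan says.** The protocol treats stopping drug and leaving the study differently. For those who only stop drug, the schedules of activities (footnote c) state: "Patients who discontinue study drug prematurely will continue to complete assessments as indicated until the end of the study". For those who leave, Section 4.6.2 states: "Patients who discontinue from study participation will have an early termination visit 7 (± 2) days after their final dose of study drug". It adds: "Patients who discontinue from the study after Day 14 will not be required to complete an early termination visit".

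Leaving need not be the patient's own decision. Section 4.6.2 says: "In addition, the investigator has the right to withdraw a patient from the study at any time". Its list of possible reasons includes adverse event and "Patient non-compliance, defined as failure to comply with protocol requirements as determined by the investigator or Sponsor".

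Two secondary efficacy endpoints count clinical events: COVID-19-related complications (which include death and hospitalization) and all-cause hospitalization or death (Protocol Section 6.4.2.2). Both belong to the mITTi population (Protocol Section 6). Protocol Section 6.4.2.2 summarises such endpoints as counts, proportions and differences, and leaves missing-data rules to the SAP. SAP Section 5.4.2.3 says: "For frequency efficacy endpoints, the number, proportion and difference in proportions between the AT-527 group and the pooled placebo group", with 80% confidence intervals. It gives no rule for patients whose follow-up is incomplete, and the SAP does not list the all-cause endpoint at all.

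**The concern.** A patient removed for non-compliance or an adverse event has not necessarily refused further contact, yet the plan schedules none beyond the early termination visit. If such a patient is later admitted to hospital or dies, the study may not learn of it. With an mITTi denominator and events counted only when recorded, that patient becomes a non-event by default.

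Patients who leave because they are unwell, do not tolerate treatment or do not comply may plausibly have a different risk from those who stay. The crude rate is then too low in each arm, and the difference is distorted if the unseen risk is not the same in both. Few events can be expected in non-hospitalized patients with mild or moderate disease, so a handful of unknown outcomes matters. The amendment rationale says the all-cause endpoint was added because these outcomes are important, and Protocol Section 6.1 presents the Cohort E sample size as helping to characterise the secondary endpoints.

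There is also an inconsistency of principle. SAP Section 5.2 keeps protocol deviators in the analysis: "Patients will not be excluded from the analysis populations based on major PDs". Keeping them in the analysis set helps little if their outcomes were not collected.

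**Working it through.** **Stated figures.** The documents give no event rate and no dropout rate for these endpoints, so there is no figure to reproduce. The only inflation for Cohort E is for SARS-CoV-2 positivity: 100/0.9 = 111.1, rounded up to 112 per arm. It contains no allowance for dropout.

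**Time without scheduled contact** (planned follow-up 33 days, Protocol Section 3.1; early termination visit at last dose + 7 ± 2 days):
- Full course, last dose Day 5 or 6: visit between Day 5 + 5 = 10 and Day 6 + 9 = 15, leaving 33 − 15 = 18 to 33 − 10 = 23 days.
- Last dose Day 3: visit on Day 8 to 12, leaving 21 to 25 days.
- Leaving on Day 15: no visit required, leaving 33 − 15 = 18 days.

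**Rules for incomplete data in the SAP, side by side:**
- Primary endpoint (5.3.2): missing values are left out.
- Virology proportion (5.4.2.1): missing values are left out, and time points after death count as positive.
- Virology and symptom time-to-event endpoints (Tables 7 and 9): censoring at the last assessment on discontinuation.
- Frequency efficacy endpoints (5.4.2.3): nothing stated.

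**Effect on one arm's rate, if leavers stay in the denominator as non-events.** Let p be the true risk, d the share leaving and f the share of leavers' risk that falls after last contact, with leavers and stayers at the same risk. Then crude rate = p × (1 − d × f). All three inputs are assumptions, with d from 2% to 10% and f from 50% to 100%:
- True 2%: 2% × (1 − 0.10 × 1) = 1.8% up to 2% × (1 − 0.02 × 0.5) = 1.98%.
- True 5%: 4.5% to 4.95%.
- True 10%: 9.0% to 9.9%.

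**Effect on the difference.** Let r be the leavers' risk. The unseen risk in an arm is u = d × r × f, and the bias in the difference is −(u₁ − u₀). It is zero when leaving and risk are equal in both arms and there is no treatment effect. Assume 10% versus 2% leaving, all their risk unseen, and leavers at three times the stayers' risk p. Then bias = −(0.10 − 0.02) × 3p = −0.24p:
- p = 2%: −0.5 points.
- p = 5%: −1.2 points.
- p = 10%: −2.4 points.

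The shift favours the arm that loses more patients.

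**Bounds (illustration).** Take 3/100 events on AT-527, 5/100 on placebo and five leavers per arm with unknown status.
- Crude difference: 3% − 5% = −2 points.
- All placebo leavers and no AT-527 leavers have events: 3% − 10% = −7 points.
- The reverse: 8% − 5% = +3 points.
- Leavers left out instead: 3/95 − 5/95 = −2.1 points, so exclusion does not resolve the uncertainty either.

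**The case against.** The strongest reply is that safety reporting already covers these patients. Protocol Sections 5.3.1 and 5.4.2.2 require adverse events to be reported until 28 days past the last dose (Day 33 or 34 after a full course), with no stated exception for leavers. Section 5.3.5.7 requires deaths in that period to be recorded, Section 5.3.5.10 makes most event-related hospitalizations serious adverse events, and Section 5.5.1 asks for each event to be followed to resolution, stability, loss or withdrawn consent. This stands in part: a reader might infer that follow-up stops altogether on leaving, and the documents do not say so. What is missing is a planned contact at which a new event in a leaver would come to light. Section 5.3.5.9 also keeps anticipated COVID-19 deterioration out of adverse event recording, so this route is not a full substitute.

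Second, no passage says that leavers are counted as event-free. That is correct: it is the default consequence of an mITTi denominator and recorded events, not a stated rule. The SAP supplied also predates the enlarged Cohort E (its Section 1.2 describes 40 patients there and about 220 in all). For the all-cause endpoint it therefore shows an update still to be made; the missing rule is demonstrable only for complications.

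Third, Section 4.6.2 permits removal for non-compliance and does not require it. Protocol Section 4.3.2 has patients resume after missed doses, and SAP Section 5.6.1 tabulates compliance below 80%, so many poor compliers may stay. This limits how often the problem arises.

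Fourth, precision is low anyway. With 3% risk and 100 per arm, the 95% half-width of the difference is 1.96 × √(2 × 0.03 × 0.97/100) = 4.7 points, larger than each bias illustrated above. That limits the practical weight of the point, but it does not justify an avoidable systematic error.

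A reader might also infer that removing non-compliers turns the viral RNA comparison into a per-protocol contrast. The documents do not support this: leavers stay in mITTi, their earlier swabs count, and SAP Section 5.1 maps early termination swabs to visit windows. Some later swabs could be lost, but no size for that can be derived.

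**Conclusion.** The point holds in this form: the plan schedules no outcome contact after at most one early visit for patients who leave, including some who have not refused contact, and it states no rule for incomplete follow-up for two clinically important proportions.

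The size is unknown. The ranges above rest on assumed event risks, shares leaving and leavers' risk. A reader might infer that the direction of the treatment difference will be reversed. That needs chosen inputs: more leavers on AT-527, at several times the stayers' risk, with none of their events seen. Nothing in the documents establishes those conditions.

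The endpoints are descriptive and secondary in a study the sponsor calls hypothesis-generating, and the point is not shown to affect the primary virology result. It is still worth correcting, because outcomes not collected cannot be recovered at the analysis stage.

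**What to change.** None of this alters any rule on when drug is stopped.

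- **Protocol Section 4.6.2.** State that non-compliance or an adverse event does not by itself end outcome follow-up. Unless the patient refuses contact, scheduled assessments continue where possible, and hospitalization, complication and vital status are obtained to Day 33 by the existing telephone call or from records.
- **SAP Section 5.4.2.3.** Add the all-cause hospitalization or death endpoint. State the denominator and the Day 33 horizon for both frequency endpoints. Report by arm how many patients have unknown status at Day 33, and give best- and worst-case bounds for the difference. Cumulative incidence may be shown as well, but censoring at last known status assumes that leavers resemble stayers, so it does not by itself remove the bias. The contact is the essential step.

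The cost is amendment and SAP wording plus a little more site follow-up for patients who leave. Some will still refuse contact, which is why the bounds are needed.
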